## **9.7 Early phase safety monitoring**

The Investigator will monitor adverse events in an ongoing manner and inform the Sponsor of any clinically relevant observations. Any required safety reviews will be made jointly between medically qualified personnel representing the Sponsor and Investigator. Such evaluations may occur verbally, but the outcome and key discussion points will be summarized in writing (e-mail) and made available to both Sponsor and all Investigator(s). Criteria pertaining to stopping the study/treatment or adapting the study design are presented above.

When two or more clinical site(s) are participating in the clinical study, the Sponsor will advise the Investigator(s) at all sites in writing (e-mail) (and by telephone if possible) of any new, clinically relevant safety information reported from another site during the conduct of the study in a timely manner.

# **10 Data review and database management**

## **10.1 Site monitoring**

Before study initiation, at a site initiation visit or at an investigator's meeting, a Novartis representative will review the protocol and data capture requirements (i.e. eSource or eCRFs) with the investigators and their staff. During the study Novartis employs several methods of ensuring protocol and GCP compliance and the quality/integrity of the sites' data. The monitor will visit the site to check the completeness of subject records, the accuracy of data capture / data entry, the adherence to the protocol and to Good Clinical Practice, the progress of enrollment, and ensure that study drug is being stored, dispensed, and accounted for according to specifications. Key study personnel must be available to assist the monitor during these visits.

Continuous remote monitoring of each site's data may be performed by Novartis or a CRO working on behalf of Novartis. Additionally, a central analytics organization may analyze data and identify risks & trends for site operational parameters, and provide reports to Novartis Clinical Teams to assist with trial oversight.

The investigator must maintain source documents for each subject in the study, consisting of case and visit notes (hospital or clinic medical records) containing demographic and medical information, laboratory data, electrocardiograms, and the results of any other tests or assessments. All information on CRFs must be traceable to these source documents in the subject's file. The investigator must also keep the original informed consent form signed by the subject (a signed copy is given to the subject).

The investigator must give the monitor access to all relevant source documents to confirm their consistency with the data capture and/or data entry. Novartis monitoring standards require full verification for the presence of informed consent, adherence to the inclusion/exclusion criteria, documentation of SAEs, and the recording of data that will be used for all primary and safety variables. Additional checks of the consistency of the source data with the CRFs are performed according to the study-specific monitoring plan. No information in source documents about the identity of the subjects will be disclosed.

## **10.2 Data collection**

Designated investigator staff will enter the data required by the protocol into the Electronic Case Report Forms using fully validated software that conforms to 21 CFR Part 11 requirements. Designated investigator site staff will not be given access to the EDC system until they have been trained. Validation checks for data discrepancies and, by generating appropriate error messages, allow the data to be confirmed or corrected before transfer of the data to Novartis or the CRO working on behalf of Novartis. The Investigator must certify that the data entered into the Electronic Case Report Forms are complete and accurate. After database lock, the investigator will receive copies of the subject data for archiving at the investigational site.

Data not requiring a separate written record will be defined in the SOM and [Assessment schedule](#) and can be recorded directly on the CRFs. All other data captured for this study will have an external originating source (either written or electronic) with the CRF not being considered as source.

All data should be recorded, handled and stored in a way that allows its accurate reporting, interpretation and verification.

## **10.3 Database management and quality control**

Novartis or designated CRO staff review the data entered into the CRFs by investigational staff for completeness and accuracy and instruct the site personnel to make any required corrections or additions. Queries are sent to the investigational site via the EDC system. Designated investigator site staff is required to respond to the query and confirm or correct the data. If the electronic query system is not used, a paper Data Query Form will be faxed to the site. Site personnel will complete and sign the faxed copy and fax it back to Novartis staff who will make the correction to the database. The signed copy of the Data Query Form is kept at the investigator site. Concomitant medications entered into the database will be coded using the WHO Drug Reference List, which employs the Anatomical Therapeutic Chemical classification system. Medical history/current medical conditions and adverse events will be coded using the Medical dictionary for regulatory activities (MedDRA) terminology.

Laboratory results will be sent electronically to Novartis (or a designated CRO).

The occurrence of relevant protocol deviations will be determined. After these actions have been completed and the database has been declared to be complete and accurate, it will be locked and made available for data analysis. Any changes to the database after that time can only be made by joint written agreement between the COAR Analytics NIBR Franchise Head and the relevant NIBR TA Head.

## **10.4 Data Monitoring Committee**

Not required.

## **10.5 Adjudication Committee**

Not required.

# **11 Data analysis**

The analysis will be conducted on all subject data at the time the trial ends. Any data analysis carried out independently by the investigator should be submitted to Novartis before publication or presentation.

## **11.1 Analysis sets**

For all analysis sets, subjects will be analyzed according to the study treatment(s) received.

The safety analysis set will include all subjects that received any study drug.  
Corporate Confidential Information

## **11.2 Subject demographics and other baseline characteristics**

All data for background and demographic variables will be listed by treatment group and subject. Summary statistics will be provided by treatment group. Relevant medical history, current medical conditions, results of laboratory screens, drug tests and any other relevant information will be listed by treatment group and subject.

## **11.3 Treatments**

Data for study drug administration (rescue medication) and concomitant therapies will be listed by treatment group and subject.

## **11.4 Analysis of the primary variable(s)**

### **11.4.1 Primary Variable(s)**

The primary efficacy endpoint will be the average of the three morning fasting free testosterone concentrations in blood.

#### **11.4.2 Statistical model, hypothesis, and method of analysis**

The primary analysis will assess the treatment effect of LIK066 on free T at Day 15. The ratio of Day 15 to baseline free T will be analyzed in an analysis of covariance model with treatment as a categorical factor and baseline free T as a covariate. Additional baseline characteristics that may be predictive of free T may be added to the model as covariates. The logarithm of the ratio and of baseline free T will be applied prior to the analysis.

The geometric mean of the ratio to baseline for free T will be estimated from the model for LIK066 and placebo, along with the treatment ratio and the associated p-value and two-sided 90% confidence interval (CI). From these quantities, the following criteria will be assessed:

1. the upper confidence limit of the 90% CI is less than 1, and
2. the estimated treatment ratio is less than 0.75.

The first criterion addresses with high certainty whether the effect of LIK066 on free T reduction is superior to placebo. The second criterion addresses whether the observed treatment effect of LIK066 on free T reduction is at least 25%. An effect size of 20-25% on hyperandrogenism is considered to be clinically meaningful in PCOS as it correlates with improved ovulation and fertility ([Harborne et al 2003](#)).

Subjects who are deemed to have hormonal evidence of ovulation during the study may be excluded from the primary analysis.

#### **11.4.3 Handling of missing values/censoring/discontinuations**

The primary efficacy analysis will be based on all subjects with an evaluable baseline and Day 15 free T profile and that have no hormonal evidence of ovulation during the study.

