Interventions that reduce serum insulin levels such as metformin, insulin-sensitizing thiazolidinediones, and weight loss result in significant improvement of hyperandrogenemia and ovulation in PCOS (Legro et al 2013). Pilot trials in PCOS with a short 10-day course of diazoxide, an inhibitor of insulin secretion, have shown significant reduction in circulating androgen levels (Nestler et al 1989). Metformin lowers insulin levels primarily by reducing hepatic glucose output and opposing glucagon-mediated signalling in the liver, and to a lesser extent by increasing glucose uptake in skeletal muscle (Pernicova and Korbonits 2014). Randomized controlled trials with metformin in PCOS have shown an improvement in androgen measures of about 20% when compared to placebo (Harborne et al 2003). Dapagliflozin, a sodium–glucose cotransporter (SGLT) 2 inhibitor approved for T2D, is currently in a phase 3 clinical trial in PCOS, with and without metformin or exenatide to evaluate the relationship of insulin resistance, body weight and effects on hyperandrogenemia

([NCT02635386](#)). There is a clear association between hyperinsulinism and hyperandrogenism in PCOS and clinical evidence that lowering insulin levels and/or increasing insulin sensitivity improve hyper androgenism and ovulation in these patients.

Sodium–glucose cotransporters (SGLT) 1 and 2 play an important role in glucose homeostasis with SGLT1 being the primary transporter responsible for absorption of glucose and galactose in the intestine, and SGLT 2 being the primary transporter responsible for renal glucose reabsorption ([Kalra 2014](#), [Sands et al 2015](#)). SGLT2 inhibitors are approved for the treatment of type 2 diabetes, acting primarily by increasing urinary glucose excretion (UGE) and improving glycemic control. Blockade of enteric SGLT1 results in glucose and galactose malabsorption ([Sands et al 2015](#)). There are no approved dual inhibitors of SGLT 1 and 2. Sotagliflozin, a dual inhibitor of SGLT1 and SGLT2, is in Phase III trials for diabetes, type 2 and type 1.

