## 4.2 Exclusion criteria

Subjects with polycystic ovary syndrome (PCOS) fulfilling any of the following criteria are not eligible for inclusion in this study:

1. Subjects with pre-existing type 1 or type 2 diabetes mellitus, Cushing's syndrome, congenital adrenal hyperplasia, ovarian or adrenal androgen-secreting tumor, uncontrolled thyroid disease, untreated obstructive sleep apnea.
2. Oophorectomy.
3. Exogenous causes of hirsutism (such as drug-induced).
4. Menstruation in the 30 days prior to screening or prior to the initiation of treatment (Day 1).
5. Pregnant or nursing (lactating) women, where pregnancy is defined as the state of a female after conception and until the termination of gestation, confirmed by a positive hCG laboratory test
6. Abnormal screening labs defined as:
  - Early morning total testosterone levels => 2.5× ULN or => 200 ng/dl
  - DHEAS > 2× ULN or > 700 mcg/dl
  - Prolactin > ULN on early AM sample (allow repeat × 1 for borderline levels, enroll based on 1 normal level)
  - 17-OHP levels (early AM sample) > 200 ng/dl
  - TSH levels > 10 uUI/ml and clinical symptoms of hypothyroidism. Subjects with sub clinical hypothyroidism do not need to be excluded. Subjects well controlled on thyroid medication can be enrolled.
7. Symptomatic genital or urinary tract infection (UTI) in the 4 weeks prior to screening or the presence of active UTI at screening
8. Ongoing participation in a weight loss program such as with exercise, diet or drugs.
9. History of significant gastrointestinal surgery that could affect intestinal glucose absorption (e.g. bariatric surgeries including, Roux-en-Y gastric bypass, sleeve gastrectomy, Nissen fundoplication); active gastrointestinal disorders such as irritable bowel syndrome and inflammatory bowel disease.
10. Clinically significant GI disorder related to malabsorption or that may affect drug or glucose absorption (e.g. swallowing disorder, severe GI motility disorder, chronic diarrhea, glucose/galactose/lactose intolerance)
11. History of hypersensitivity to the study drug (active or placebo), or to drugs of similar chemical classes. Ingredients of the study drug are described in Section 3.2.1 of the Investigators' Brochure.
12. Use of prohibited medications, including:
  - antidiabetic medications or weight loss drugs within 3 months of screening.

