#### **11.4.4 Sensitivity analyses**

As a sensitivity analysis, the change from baseline in free T at Day 15 will be analyzed in an analysis of covariance model of the same form as the one specified for the primary analysis, except no logarithmic transformation will be applied. The least-squares mean change from baseline will be estimated from the model for LIK066 and placebo, along with the treatment difference and the associated p-value and two-sided 90% confidence interval.

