## **6 Statistical methods for Pharmacodynamic (PD) parameters**

All subjects within the primary PD analysis set will be included in the PD data analysis, unless otherwise stated.

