#### **6.1.3.1 Handling of missing values/censoring/discontinuations**

The primary efficacy analysis will be based on all subjects with an evaluable baseline and Day 15 free T profile who have no hormonal evidence of ovulation during the study. If one or two of the three morning measurement are missing, the average of observed measurements will be used. If all are missing, there will be no imputation of the missing data.

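### Excluding women who ovulate from the primary analysis is optional in one section and mandatory in the next, so the plan permits two primary populations

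*Protocol*

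**What the plan says.** On women who ovulate, the wording alternates:

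- **Optional.** Protocol 11.4.2: "Subjects who are deemed to have hormonal evidence of ovulation during the study may be excluded from the primary analysis". SAP 6.1.3 carries the same sentence.
- **Mandatory.** Protocol 11.4.3 bases the primary analysis on "all subjects with an evaluable baseline and Day 15 free T profile and that have no hormonal evidence of ovulation during the study". SAP 6.1.3.1 likewise limits it to subjects "who have no hormonal evidence of ovulation during the study".
- **Conditional.** The protocol summary, Protocol 3.1 and SAP 1.4 allow extra enrolment if more than 2 subjects bleed, in case those women are dropped from the PD analysis set after progesterone confirms ovulation.
- **Silent.** The PD set defined in SAP 4 does not mention ovulation, and the visible deviation codes in SAP Table 4-1 include none for it. SAP 6 adds: "All subjects within the primary PD analysis set will be included in the PD data analysis, unless otherwise stated".

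The only visible sensitivity analysis (Protocol 11.4.4, SAP 6.1.3.2) reuses the primary model, "except no logarithmic transformation will be applied". It does not change the population.

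**The concern.** The primary result is a two-part verdict: the upper 90% confidence limit is below 1, and the estimated ratio is below 0.75. With 12 women per arm, two or three exclusions can change it. The plan leaves open whether those exclusions are made.

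The choice is not neutral, because ovulation after dosing may be affected by treatment. Protocol 1.1 cites "clinical evidence that lowering insulin levels and/or increasing insulin sensitivity improve hyper androgenism and ovulation in these patients", and Protocol 11.4.2 justifies the target effect because "it correlates with improved ovulation and fertility". Removing women for an outcome that treatment may influence can bias the randomised comparison, and optional top-up enrolment restores numbers but not that comparison. No visible analysis would give the reader a free testosterone ratio and interval with these women included.

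**Working it through.** **1. Do the passages reconcile?** Protocol 11.4.3 could be read as narrowing 11.4.2. But one sentence leaves a choice and the other leaves none, neither refers to the other, and the SAP reproduces both. SAP 6 defers to whatever is stated elsewhere, and the two places that state something disagree. Two populations are therefore permitted.

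**2. Inputs (Protocol 11.7).** Baseline free testosterone has mean 79 and SD 40 pmol/L. The placebo change is -2%, the correlation 0.5, the effect 35% over placebo (ratio 0.65), with 12 per arm.

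- Log-scale SD = sqrt(ln(1 + (40/79)²)) = 0.478
- Residual SD = 0.478 × sqrt(1 - 0.5²) = 0.414
- Standard error of the log ratio = 0.414 × sqrt(2/12) = 0.169
- Expected 90% CI, with 24 - 3 = 21 degrees of freedom: 0.65 × exp(±1.721 × 0.169) = 0.49 to 0.87

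**3. The plan's own figures.** Simulating the log-scale ANCOVA with both criteria gives 78.4% to 78.6% if the effect is read as 0.63/0.98 and the correlation as raw-scale. That is within 2 points of the stated 80%. Other readings give 75% to 77%. The illustration below uses a ratio of 0.65 and a log-scale correlation, for which success is about 76%. With no true effect, both criteria are met in 3.7% to 3.9% of trials; the stated 5% matches the first criterion alone.

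**4. Effect of exclusion.** The documents give no ovulation rate, so the rates and slopes are assumptions. I used logit P(ovulation) = a + b × ln(Day 15/baseline), with the same a and b in both arms, b = 0, -1 or -3, and a set to give 8% on placebo. That is about 2 of 24, the bleeding count in the top-up rule, and not an expected ovulation rate. The LIK066 rate then follows from the free testosterone effect. Expected exclusions are 12 × 0.08 + 12 × 0.12 = 2.4 at the lower rate and about 3.3 at the upper (unrounded rates). Each simulated trial was analysed with and without ovulators, with no top-up and 40,000 to 100,000 runs per setting.

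| Setting (placebo / LIK066 rate) | Mean ratio | Success | Opposite verdicts |
|---|---|---|---|
| All subjects kept | 0.65 | 76% | – |
| Excluded, 8% / 8%, unrelated to free T | 0.65 | 73% | 8% |
| Excluded, 8% / 12%, b = -1 | 0.654 | 71% | 10% |
| Excluded, 8% / 20%, b = -3 | 0.680 | 64% | 17% |
| Dropped at random, 8% / 12% | 0.65 | – | 9% |
| Dropped at random, 8% / 20% | 0.65 | – | 12% |

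Opposite verdicts mean that one population meets both criteria and the other does not. In the two related settings, the all-subjects analysis passes and the no-ovulation analysis fails in 7% to 14% of trials; the reverse happens in about 3%. The random-drop rows show how much comes from smaller numbers alone: 9 of the 10 points, and 12 of the 17.

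**5. Range.** With 4% on placebo, the ratio is 0.653 to 0.669 and verdicts differ in 6% to 11% of trials. With 15%, these are 0.656 to 0.692 and 15% to 25%. With one-for-one top-up to a cap of 30, success in the 8% setting is 73% to 68%.

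**6. No true effect.** At the 8% placebo rate, false success is about 4% in either population, and about 5% if whichever passes is taken.

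**7. Direction.** Suppose instead that LIK066 raises ovulation to 20% to 25% against 5% on placebo, separately from its effect on free testosterone. If ovulators have lower free testosterone, exclusion moves 0.65 to between 0.68 and 0.72. If they have higher free testosterone, it moves a true ratio of 1.00 to between 0.90 and 0.95, and false success rises to about 7% to 11%. Neither pattern can be confirmed or ruled out from the documents.

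The SAP's body weight covariate was not simulated.

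**The case against.** Several points on the other side stand.

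- **Not all excluded ovulation follows randomisation.** The wording covers the whole study, and Protocol 3.1 includes screening and a baseline visit. Progesterone has a baseline value (SAP 6.2.1). Removing a woman whose baseline value already shows ovulation does not bias the comparison.
- **A no-ovulation primary population is defensible.** The study is mechanistic and non-confirmatory. Recent menstruation bars entry (Protocol 4.2, criterion 4), and deviation from that criterion removes a subject from the PD set (SAP Table 4-1). That entry rule may also keep ovulation rates low.
- **Related androgens are partly covered.** SAP 6.2.3 plans treatment ratios with 90% intervals for total testosterone, SHBG and free androgen index, with no ovulation exclusion stated. This mitigates in part, but it does not cover free testosterone, and the women could still be removed from the PD set under SAP 1.4.
- **Redaction.** The PD set in Protocol 11.1, part of SAP Table 4-1 and other SAP sections are withheld. An ovulation rule or a supplementary analysis may sit there.

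A reader might infer that exclusion favours LIK066 or inflates false success. The documents do not support that: under a shared rule linking ovulation to free testosterone, the shift is towards no effect. Nor do they support the opposite certainty, since Protocol 1.1 describes a possible insulin effect on LH and no ovulation data are given. A reader might also take the 10% to 17% disagreement as bias; most of it is smaller numbers.

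**Conclusion.** The contradiction is certain: it appears in consecutive sections of both documents and concerns the primary analysis. The absence of a model-based all-subjects analysis of free testosterone can be asserted only for the visible text.

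The consequences are modest. Under the assumed rates the ratio shifts by at most 0.03 (0.680 - 0.65), small beside an expected interval of 0.49 to 0.87. Success falls by 5 to 12 points (76% to 71% or 64%), part of it from fewer subjects. These sizes rest on assumed ovulation rates and slopes, on all excluded ovulation being tied to the on-treatment change, and on no top-up. The ambiguity matters even without bias: at 8% in both arms, unrelated to free testosterone, the two populations still disagree in about 8% of trials. It should be fixed, but it does not undermine the trial.

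**What to change.** 1. State one rule, in identical words, in Protocol 11.4.2 and 11.4.3 and SAP 6.1.3 and 6.1.3.1. Align the protocol summary, Protocol 3.1, SAP 1.4 and the PD set definition with it. Either population is defensible as primary: all subjects preserves the randomised comparison, while the no-ovulation set addresses the mechanistic question with less cycle-related noise.
2. Run the same log-scale ANCOVA in the other population, reporting the treatment ratio, 90% CI and both criteria, as a named sensitivity analysis in Protocol 11.4.4 and SAP 6.1.3.2.
3. Classify ovulation before treatment codes are seen, by a progesterone rule and sampling window fixed in advance (unless the redacted text already has them). Separate evidence at baseline from evidence after dosing, and report counts by arm.

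The cost is wording and one extra model run, with no new visits or samples. The drawback is a few Day 15 values with cycle-related variability in the all-subjects analysis, which the no-ovulation analysis alongside would show.
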